of Alzheimer's disease (AD) (20, 21) and AD patients with epilepsy (80). LEV improves pattern recognition memory in patients with mild cognitive impairment (MCI) (13, 14).

Neurobiologically, low dose LEV reduces hippocampal hyperactivity both in rodent models of AD (20, 21) as well as in patients with MCI (13, 14). Motivated by this finding, we examined LEV effects in the DBA/2 mouse model of schizophrenia. The measure of hippocampal inhibitory function used was P20-N40 event-related potential (ERP) auditory gating, the mouse equivalent of the human P50 auditory gating paradigm, a widely used measure of human inhibitory neuronal function. Deficits in P50 gating (the ability of neuronal circuits to reduce early post-stimulus response to the second of a pair of identical, repeated clicks) are theorized to be due to dysfunction in inhibitory circuitry in the hippocampus, with drug effects on rodent gating being highly predictive of human effects (e.g. as with DMXB-A (81-83)). We found that a low LEV dose was associated with improved inhibitory gating (22). In summary, these preliminary data, along with prior reports of LEV effects on both hippocampal activity in different patient populations as well as its pro-cognitive effects in epilepsy, provide strong preliminary support for the proposal hypothesis.

IV. Research Methods

A. Outcome Measure(s):

Primary Endpoint

- 1) The effects of 4 weeks of LEV vs. placebo treatment on cognitive function (RBANS Total Scale score).

Secondary (Exploratory) Endpoints

- 1) The effects of 4 weeks of LEV vs. placebo on resting hippocampal activity.
- 2) Correlation between the effects of 4 weeks of LEV on cognitive function and the effects of LEV on resting hippocampal activity.
- 3) The effects of LEV vs. placebo on individual cognitive assessment domains (e.g. Attention).
- 4) The effects of LEV vs. placebo on clinical symptoms (BPRS/SANS/GAF/AIMS).
- 5) The effects of LEV vs. placebo on hippocampal CBF, measured by arterial spin labeling (ASL).
- 6) The effects of LEV on hippocampal and selective-attention-related neuronal activity.
- 7) The effects of LEV on hippocampal activity during a memory task (pattern separation).
- 8) Side effects and tolerability.
- 9) Treatment (drug or placebo) X smoking status (smoker or non-smoker) interaction effects.
- 10) The effects of LEV vs. placebo on eating behaviors (TFEQ/FCQ/PFS/VAS) will also be assessed as exploratory aims, given potential LEV effects on appetite (114).

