The first study visit will include written informed consent and study screening. This visit will take place at either the VA Hospital, the UCD Clinical Translational Research Center (CTRC), Brain Imaging Center (BIC), and/or Schizophrenia Research Center, depending on what works best for participant convenience and scheduling. Measures may be administered remotely (via phone or video call) when possible. Screening measures will include a physical exam with a medical history review (or based on results from a physical exam within the last 6 months), measures of vital signs, a hearing test, demographics form, the Annett Handedness Questionnaire, the Fagerstrom Test for Nicotine Dependence, a smoking history questionnaire; a carbon monoxide breath test (to test for nicotine use; this may be omitted due to COVID-19 precautions), completion of an MRI screening form, the COVID-19 Impact Questionnaire, the Brief Psychiatric Rating Scale (BPRS), the Abnormal Involuntary Movement Scale (AIMS, completed if time allows and may also be repeated on future study days upon study doctor recommendation), the “Baseline” version of the Columbia Suicide Severity Rating Scale (C-SSRS), a blood sample (if results on renal function are not available within the last year), and a urine sample to test for substance use and pregnancy (if applicable). If a participant is unsure about the presence of metal in his/her body, an x-ray may be done to confirm appropriateness for MRI scanning. Blood samples will be taken by trained phlebotomists or nurses. If the blood sample is taken at the VA, it will be analyzed by the VA lab; if it is taken at the CTRC, it will be analyzed by the CTRC or UCH labs (as applicable for each test). Study research staff will perform the simple urine toxicology screen and pregnancy test. Subject payments will be in the form of agent cashier vouchers.

Baseline Study Day

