If participants are deemed eligible for the study after the screening measures have been completed, they will be asked to come back approximately one week later for the Baseline Study Day. Subjects will arrive at the Anschutz Medical Campus (AMC; all Study Days will take place here because MRI scanning will be performed at the Brain Imaging Center, located on the Anschutz Medical Campus) in the morning in a fasted state (not having eaten for at least approximately 2 hours). Baseline Study Day procedures will include the following measures/assessments: side effects questionnaires, vital signs, weight, urine screen for substance use and/or pregnancy (if applicable), a carbon monoxide breath test (may be omitted due to COVID-19 precautions), concomitant medications form, AIMS (if recommended by the study physician, time permitting) clinical measures (BPRS, SANS, GAF, C-SSRS), food-related questionnaires (Three Factor Eating Questionnaire [TFEQ], Food Craving Questionnaire [FCQ], Power of Food Scale [PFS], Visual Analogue Scales of hunger, satiety, prospective food consumption [VAS]), and the RBANS cognitive test battery. A medical exam will only be completed on the Baseline Study Day if more than 60 days have elapsed since the screening visit and it is deemed necessary by the study physician. Participants will also complete an MRI scanning session, which will last approximately one hour. The MRI scan will include an anatomical MRI scan, a resting-state fMRI scan, and fMRI scanning during sensory/cognitive tasks. Soon after MRI scanning, participants will complete a post MRI questionnaire and will be given their first pill (LEV or placebo, depending on randomized treatment order). Approximately one hour after taking it, they will complete a second MRI scan. The purpose of this is to assess

acute response to treatment. The ~one-hour period approximately captures peak LEV absorption (Patsalos, 2000). After the second MRI, participants will be given breakfast.

Treatment Arm 1

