After all Baseline Study Day procedures have been completed, participants will be given a ~2-week supply of either LEV (oral capsule) or placebo (oral capsule), depending on their treatment order assignment, with instructions to take the pills BID. Subjects will be given a pill log and written study instructions. Study staff will call participants within ~1 week after starting taking pills to administer a side effects questionnaire and the C-SSRS over the phone. ~2 weeks after starting the pills, participants will come in for a check-in visit (Check-in #1). This check-in visit will either take place at the VA or at the UCD CTRC, depending on what works best for participant convenience. During this visit, they will give their completed pill log to the researcher and the pill vial they were given (including any remaining pills that were not taken). Participants will complete a side effects questionnaire, clinical measures (BPRS, C-SSRS), and a concomitant medications form. They will also have their weight and vital signs measured. It would also be acceptable to administer this visit virtually via phone or video call, to minimize in-person visits. In this case, vital signs and weight measures may be omitted from this check-in visit, but all other measures would be administered virtually. At the end of this visit, participants will be given the next ~2-week supply of pills, to complete the ~4-week treatment period. If the visit is conducted virtually, a member of the research team may deliver the next ~2-week supply of pills to the participant and pick up the completed pill log. Participants will also be called by study staff during this next ~2-week period to assess side effects over the phone.

Post-Intervention 1 Study Day (“Study Day 1”)

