Description: Patients will be assessed for their current severity of clinical symptomatology using the Brief Psychiatric Rating Scale (BPRS), the Scale for the Assessment of Negative Symptoms (SANS), Global Assessment of Function (GAF), Abnormal Involuntary Movement Scale (AIMS), and the Columbia Suicide Severity Rating Scale (C-SSRS; baseline and “since last visit” versions). The BPRS is an interview that asks questions about somatic concerns, anxiety, guilt feelings, grandiosity, depressive mood, hostility, suspiciousness, hallucinations, and unusual thought content while observing the behavior, affect, and cognitive clarity of the subject. The SANS assesses five symptom complexes to obtain clinical ratings of negative symptoms in patients with schizophrenia and schizoaffective disorder. They are: affective blunting; alogia (impoverished thinking); avolition/apathy; anhedonia/asociality; and disturbance of attention. The GAF Scale is a 100-point scale that measures a patient’s overall level of psychological, social, and occupational functioning on a hypothetical continuum. The AIMS records the occurrence of Tardive Dyskinesia (TD) in patients receiving neuroleptic medications and follows the severity of a patient’s TD over time. Both versions of the C-SSRS are used for suicidal ideation assessment.

Risks: The questionnaires may cause fatigue, tiredness, and emotional discomfort. A previously unknown psychiatric disorder or symptom may be revealed during the interview. Should the subject request to be referred for further treatment for these newly discovered symptoms, the information will then become a part of the participant’s medical record, and insurance companies will have access to this record, potentially affecting their ability to gain access to health or other insurance.

Justification: A staff member on the protocol who is blind to treatment status will administer all symptom measures. All of these symptom measures have been clinically validated in schizophrenia and schizoaffective disorder. The study subject may request to be referred for further evaluation and treatment. The discovery of new symptoms or disorders leads to the potential for better psychiatric treatment and care for the subject.

fMRI

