Justification: The RBANS is simple to administer and is done so by trained personnel. The RBANS has been clinically validated and is a standard tool for assessing changes in cognition in clinical trials of schizophrenia (99). Study personnel have experience administering the RBANS, and it has been recently used in a published phase II clinical trial in schizophrenia by members of the study team (81).

Drug

The drug to be used in this study is (S)- α -ethyl-2-oxo-pyrrolidine acetamide (Levetiracetam, also known as Keppra). This drug is structurally similar to Piracetam, a synthetic derivative of the inhibitory neurotransmitter GABA. It can be administered orally and is typically prescribed for the management of seizures in doses from 500-1500 mg (31).

Risks: LEV is generally well tolerated at the lowest clinically-used of 3,000 mg/day. As such, using ultra-low dose of 125 mg BID is expected to be extremely well tolerated. The most common side effects are drowsiness, asthenia, and dizziness. More rare side effects are insomnia, anorexia, rhinitis, depression, nervousness, mood swings, ataxia, vertigo, amnesia anxiety, and hostility. LEV has no known drug interactions. Side effects will be monitored during the trial on a weekly basis. Stopping and subject withdrawal criteria are described in Study Design and Research Methods.

E. Potential Scientific Problems:

None.

F. Data Analysis Plan:

RBANS

The RBANS has a total scale score and 5 index scores. The scores are scaled with a mean of 100 and a standard deviation of 15. Comparisons (LEV vs. placebo) will be performed using mixed-effects, repeated measures models.

fMRI

The fMRI data will be preprocessed using fMRIprep (Esteban et al., 2019). Condition effects (LEV vs. placebo) will be analyzed using mixed-effects, repeated measures models. Mean hippocampal BOLD response will be examined using an anatomically defined region of interest.

Clinical Symptoms

Effects of drug on BPRS, C-SSRS, SANS, GAF, and AIMS scores in patients will be evaluated using two-tailed paired t-tests. Effects of drug on total scores (e.g. total SANS, total BPRS) will be considered significant at a threshold of $p < 0.05$. Effects of drug on symptom subscales (e.g. SANS alogia) will be considered significant using a multiple comparisons-corrected threshold.

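### The C-SSRS, used to assess suicidal ideation, is analysed only by a paired t-test on an undefined score, which can drop or mask cases and gives no count by treatment

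*Combined protocol and SAP*

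**What the plan says.** Section IV.D (Symptom Measures/Questionnaires) gives the purpose of the scale: "Both versions of the C-SSRS are used for suicidal ideation assessment".

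The scale is given at Screening, on all four Study Days and at both check-ins, where "Participants will complete a side effects questionnaire, clinical measures (BPRS, C-SSRS), and a concomitant medications form". In each treatment period staff also telephone within about a week of the first pills "to administer a side effects questionnaire and the C-SSRS over the phone". Each period therefore has three on-treatment readings: the week-1 call, the check-in, and Study Day 1 or Study Day 3.

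Section IV.F has three headings: RBANS, fMRI and Clinical Symptoms. The C-SSRS appears once, under the third: "Effects of drug on BPRS, C-SSRS, SANS, GAF, and AIMS scores in patients will be evaluated using two-tailed paired t-tests". The total scores given there as examples are those of the SANS and the BPRS.

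Among the secondary (exploratory) endpoints in section IV.A, item 4 reads "The effects of LEV vs. placebo on clinical symptoms (BPRS/SANS/GAF/AIMS)" and leaves out the C-SSRS. Item 8 is "Side effects and tolerability", for which section IV.F gives no analysis.

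**The concern.** Section IV.F does not say which C-SSRS score is meant, or which of the three readings in a period enters the pair. It groups a suicidality instrument with symptom rating scales and compares means.

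Suicidal ideation in a small crossover trial is likely to be sparse, with most within-person differences at zero. A reader then needs to know how many participants had ideation on LEV, how many on placebo, how severe it was and when it occurred. A mean difference with a p-value answers none of these, and a participant without a reading under both treatments does not enter it at all.

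Section IV.D (Drug) lists depression and mood swings among the rarer side effects of LEV, so the comparison by treatment is relevant even though the scale is exploratory.

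**Working it through.** **Inputs.** The plan has no figure to reproduce: the documents give no sample size, C-SSRS scoring, event rate or SD. The illustration assumes N = 30, with N = 20 and 40 as a range, and illustrative scores. Let d be a participant's LEV score minus placebo score. All participants not mentioned have d = 0.

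**Formula.** t = mean(d) / (SD(d)/√N), on N − 1 degrees of freedom, two-sided. For k cases of equal size s on LEV and none on placebo, mean = ks/N and SD² = s²k(N − k)/[N(N − 1)]. Hence t = √[k(N − 1)/(N − k)]. The score s cancels, so p is the same whether each case scores 1 or 5.

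**1. Reference case: 3 v 0, equal scores, N = 30.** t = √(3 × 29/27) = √3.222 = 1.795, p = 0.083. At N = 20 and 40, p is also 0.083.

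**2. One of the three cases withdraws in period 1.** That person has no placebo reading and leaves the test, giving 2 v 0 at N = 29. t = √(2 × 28/27) = √2.074 = 1.440, p = 0.161. Starting from N = 20 or 40, p becomes 0.163 or 0.160. Under Possible Adverse Events, a serious adverse event leads to withdrawal, so a serious case is one that can be lost this way.

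**3. One of the three cases is more severe, N = 30.**
- Scores 1, 1, 2: mean = 4/30 = 0.133; variance = (6 − 16/30)/29 = 0.1885; SE = √(0.1885/30) = 0.0793; t = 1.68, p = 0.103.
- Scores 1, 1, 5: mean = 7/30 = 0.233; variance = (27 − 49/30)/29 = 0.8747; SE = √(0.8747/30) = 0.1708; t = 1.37, p = 0.182 (0.185 at N = 20, 0.181 at N = 40).

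The worse case raises the SD faster than the mean, so the evidence appears weaker.

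**4. Severity and number cancel.** One case scores 5 on LEV and five others score 1 on placebo. The sum of d is 5 − 5 = 0, so t = 0 and p = 1.0 at N = 20, 30 and 40.

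**5. What a count would show.** Exact (Clopper-Pearson) 95% intervals for 3 v 0:

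| N | LEV | Placebo |
|---|---|---|
| 20 | 3/20: 3.2–37.9% | 0/20: 0–16.8% |
| 30 | 3/30: 2.1–26.5% | 0/30: 0–11.6% |
| 40 | 3/40: 1.6–20.4% | 0/40: 0–8.8% |

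In scenario 2 the withdrawn case stays in the LEV count if a reading showed the ideation: 3/30 v 0/29, where the upper limit for 0/29 is 1 − 0.025^(1/29) = 11.9%. In scenario 4 the table shows 1/30 v 5/30 and the listing shows the single severe case.

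**6. Would another test repair it?** No. The exact McNemar test for 3 v 0 gives 2 × 0.5³ = 0.25, which is less sensitive than the t-test. The remedy is description, not another p-value.

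**The case against.** The strongest reply is that this is a slice of a wider gap. Section IV.F is brief for every outcome and specifies no tables or listings at all, and silence is not a decision to withhold counts. Endpoint 8 lacks any analysis. SD inflation and loss of unpaired participants affect every paired t-test. The scale is named in no endpoint, recently unstable patients are excluded, and the protocol expects this dose to be extremely well tolerated. All of that stands, and it limits the weight of the point. It does not remove it: for the C-SSRS the plan does state an analysis, and that analysis can drop or mask exactly the cases that matter.

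Three stronger readings are tempting and are not supported:
- **That suicidality goes unmonitored.** Side effects are recorded weekly, withdrawal rules exist, and staff see each C-SSRS result.
- **That p is unrelated to the number of cases.** With equal scores, others at zero and N = 30, p falls steadily for 1 to 5 cases v 0: 0.326, 0.161, 0.083, 0.043, 0.023.
- **That one fixed 3 v 0 pattern can give anything from 0.030 to 0.293.** Those values arise for three LEV cases at +2 when two other participants differ by +1 or by −1. If those two otherwise score zero, the patterns are 5 v 0 and 3 v 2, and the test is responding to real treatment information.

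**Conclusion.** The point holds as a weakness in how an exploratory safety measure is analysed and reported, and it should be corrected. The textual part rests on no assumption: the score is undefined, the reading used is unspecified, the paired t-test is the only stated analysis, and section IV.F gives no count or listing.

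The size is illustrative. At an assumed N = 30, p moves from 0.083 to 0.161 when one of three LEV cases is lost to withdrawal, or to 0.182 when one case is five times as severe as the others. A single severe LEV case can be cancelled entirely (p = 1.0) by five mild placebo cases. These results change little between N = 20 and N = 40, but they depend on the assumed scores and on all remaining differences being zero. None of them estimates what the trial will observe.

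**What to change.** Take the C-SSRS out of the paired t-tests and report it under endpoint 8:

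- Define the C-SSRS result used: ideation, and behaviour if the version records it.
- For each participant and treatment period, take the worst on-treatment result over the week-1 call, the check-in and the Study Day. These contacts are the same in both periods.
- Report, by treatment and period, the number with any ideation (or behaviour, if recorded) over the number exposed, with exact intervals.
- Include withdrawn participants with the readings they have.
- List every case with treatment, period, timing, and its pre-treatment and Study Day 2 readings, so that ideation persisting from period 1 is not read as an onset in period 2.
- Rest no safety conclusion on a p-value.

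A count of new or worsened cases is optional, and only if the look-back of each C-SSRS version used is stated. Of participants found eligible at Screening the protocol says "they will be asked to come back approximately one week later for the Baseline Study Day", while Study Day 2 follows a washout of about four weeks. A since-last-visit reading would therefore cover unequal spans, and the documents do not give the look-back of the version used at Screening.

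The cost is a few lines of SAP text, one table and one listing, all from readings already scheduled, and the loss of a formal test for this scale. No C-SSRS at early withdrawal is specified, so a withdrawn participant contributes only the contacts completed.

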As first observed by Liddle et al. (43), greater hippocampal regional cerebral blood flow (rCBF) in schizophrenia patients, relative to healthy comparison subjects, has been frequently reported (7-9, 44). Activity in the region has also been shown to correlate with the severity of psychotic symptoms (8, 43, 45). High-resolution measures of cerebral blood volume (8) and blood flow (46) have replicated and extended these findings. Furthermore, Schobel and colleagues have shown that basal blood volume in the hippocampus not only is greater in schizophrenia patients, but that the response predicts clinical progression to psychosis from a prodromal state (8, 9), suggesting that increased blood volume in the region is not a consequence of antipsychotic medication.

In addition to its target indications, LEV has a number of additional desirable pharmacologic, pharmacokinetic, and toxicological properties. Unlike many antiepileptic agents, LEV has a wide therapeutic index, with a large separation between the doses necessary to control seizures and those producing toxicity (Klitgaard et al., 1998). It has a very low potential for drug interactions, as it is not metabolized in the liver and is not significantly protein bound (<10%) (Patsalos and Sander, 1994; Perucca and Bialer, 1996); it is therefore unlikely to directly interact with antipsychotic medication. It is rapidly and almost completely (95%) absorbed following oral administration, with an oral bioavailability of close to 100% (Patsalos, 2000). LEV readily crosses the blood-brain barrier (Doheny et al., 1999; Tong and Patsalos, 2001). LEV is typically administered in twice-daily doses of 500-1500 mg for the treatment of epilepsy; these doses are generally well tolerated (Patsalos, 2000). Most relevant to the proposed study, LEV (62.5 -125 mg BID, two week administration) reduces hippocampal hyperactivity and improves cognition in patients with mild cognitive impairment (MCI) (Bakker et al., 2012).

In conclusion, based on previous studies showing efficacy in a clinical population and low toxicity, we hypothesize that LEV will reduce hippocampal hyperactivity and improve cognition in patients with schizophrenia, with a very low risk of side effects.

III. Preliminary Studies/Progress Report:

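### The corrected threshold for symptom subscales ignores the direction of effect, so on the natural reading it makes worsening of BPRS anxiety, depressive mood or hostility harder to detect; an unadjusted estimate with an interval would be a cheap improvement

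*Combined protocol and SAP*

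**What the plan says.** Section IV.F, Clinical Symptoms, covers BPRS, C-SSRS, SANS, GAF and AIMS together. Drug effects on them "will be evaluated using two-tailed paired t-tests". Total scores, with total SANS and total BPRS as examples, are judged at an uncorrected 0.05. For components the rule is: "Effects of drug on symptom subscales (e.g. SANS alogia) will be considered significant using a multiple comparisons-corrected threshold". The correction method, the set of tests it covers and their number are not given, and nothing separates improvement from worsening.

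Two other places bear on this rule:

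- **Section IV.D, Symptom Measures/Questionnaires.** The BPRS is described by its interview content: "The BPRS is an interview that asks questions about somatic concerns, anxiety, guilt feelings, grandiosity, depressive mood, hostility, suspiciousness, hallucinations", followed by unusual thought content. For the negative-symptom scale, "The SANS assesses five symptom complexes". A staff member blind to treatment administers all symptom measures.
- **Section IV.D, Drug, Risks.** "More rare side effects are insomnia, anorexia, rhinitis, depression, nervousness, mood swings, ataxia, vertigo, amnesia anxiety, and hostility".

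The Background (section II) ends with the hypothesis that the drug will "improve cognition in patients with schizophrenia, with a very low risk of side effects". Side effects and tolerability is the eighth secondary (exploratory) endpoint in IV.A. IV.F describes no analysis for it.

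**The concern.** A multiplicity correction protects against claiming a benefit by chance when many components are tested. For a harm already on the drug's side-effect list, the costly error is the opposite one: failing to see a real worsening. A single corrected two-tailed threshold applied in both directions buys protection against the first error by increasing the second.

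Three BPRS topics (anxiety, depressive mood, hostility) match listed side effects. They are rated blind under both treatments in the same people, so they are good comparative data on those harms. If the only planned statement about them is whether a corrected test was passed, a moderate worsening could appear in the report simply as not significant. A reader could not tell an estimate near zero from an imprecise estimate of real harm. In a trial of patients with psychosis that expects few side effects, that distinction matters.

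**Working it through.** **Is there a figure to reproduce?** No. The documents give no sample size, effect size, standard deviation or number of subscale tests, so the check shows a range under stated assumptions.

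**Inputs from the documents**
- Test: two-tailed paired t-test (IV.F).
- Design: two-treatment crossover, so each completer gives one LEV-minus-placebo difference (IV.C).
- Uncorrected level: 0.05, as used for total scores (IV.F).
- SANS complexes: 5. BPRS interview topics named: 9 (IV.D).

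**Assumptions**
- Completers n = 20, 30, 40 or 60.
- Bonferroni correction over m tests: m = 5 (one scale's worth, the size of the SANS set) or m = 5 + 9 = 14 (SANS complexes plus named BPRS topics).
- True worsening of 0.5 SD of the paired difference.

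**Formula.** The test level is 0.05/m, which gives 0.05, 0.05/5 = 0.010 and 0.05/14 = 0.0036. The test statistic follows a noncentral t distribution with n − 1 degrees of freedom and noncentrality 0.5 × √n. The miss rate is 1 − power.

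**Example, n = 30.** The noncentrality is 0.5 × √30 = 2.74. The critical values are 2.05 (uncorrected), 2.76 (m = 5) and 3.17 (m = 14). With five tests the critical value almost equals the noncentrality, so detection is close to a coin toss.

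| Completers | Missed, uncorrected | Missed, m = 5 | Missed, m = 14 |
|---|---|---|---|
| 20 | 44% | 70% | 82% |
| 30 | 25% | 50% | 65% |
| 40 | 13% | 33% | 47% |
| 60 | 3% | 12% | 21% |

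Power first reaches 50% at n = 30 for m = 5 and n = 39 for m = 14. For 80% power, 34 completers suffice without correction, against 51 (m = 5) or 61 (m = 14) with it.

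**Sensitivity to the meaning of half an SD.** If it means 0.5 SD of the raw score, with an assumed within-person correlation of 0.7, the standardised paired difference is 0.5/√(2 × (1 − 0.7)) = 0.645. At n = 30 the miss rates are then 7% uncorrected, 23% (m = 5) and 36% (m = 14). The levels fall, but the correction still raises the miss rate.

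**Does the uncorrected total BPRS cover the gap?** Only weakly. Suppose 3 of an assumed 18 items shift by 0.5 SD of the difference. Power of the total-score test at n = 30 is then about 47% if item differences are uncorrelated and about 15% if their correlation is 0.2.

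**The case against.** The strongest objection is that the rule may not reach these items. IV.F speaks of symptom subscales and its one example is SANS alogia. IV.D gives the SANS five complexes but describes the BPRS by interview topics, without calling them subscales. This stands as a limit: coverage of BPRS components is an inference. It is still the natural reading, because the preceding sentences treat BPRS and SANS together and the SANS item is offered only as an example. If the rule does not cover the BPRS components, IV.F states no component-level analysis for them at all, and the same edit is useful.

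A second objection is that the size is all assumption. That is fair. A reader might infer that a half-SD worsening would usually be missed. The documents do not support that: under these assumptions it holds only below about 30 to 39 completers, and it depends on an unstated sample size, family and correction method. A method less strict than Bonferroni would also cost less power. Part of the miss rate comes from sample size alone, since 44% are missed at n = 20 with no correction.

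A third objection is that safety is followed by other routes. Total BPRS is tested at an uncorrected 0.05. A weekly questionnaire asks about anxiety and depression among other symptoms, although hostility is not named in the protocol's list. IV.C also has individual withdrawal criteria that include severe agitation or hostility, and a rule that stops the trial if two or more participants have drug-related effects worse than moderate. None of the last three needs a significance test. A reader might therefore infer that the low-risk hypothesis goes unchallenged, and that inference is wrong. Nor does any passage say that a non-significant component will be reported as proof of tolerability. These routes find individual or severe events, however. They do not estimate an average difference between LEV and placebo.

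**Conclusion.** The point holds as a cheap improvement to IV.F and does not show that the plan's safety monitoring fails. A corrected two-tailed threshold used in both directions lowers the chance of detecting worsening on components that match listed side effects, and IV.F offers no estimate with an interval to offset this. For a shift of 0.5 SD of the paired difference, the correction adds about 25 to 40 percentage points to the miss rate at 30 completers (25% to 50–65%) and about 9 to 18 points at 60 (3% to 12–21%). These sizes rest on the assumed number of completers, 5 to 14 tests and Bonferroni, and on reading the rule as covering BPRS components. The direction of the effect does not depend on the first two. The missing analysis for the side-effects endpoint is background here and does not carry the point.

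**What to change.** In IV.F, Clinical Symptoms:

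1. Say that the multiplicity-corrected threshold applies to claims of symptom improvement. Name the scales and components in the family and the correction method.
2. For BPRS hostility, anxiety and depressive mood, report the LEV-minus-placebo difference with an unadjusted 95% confidence interval, and the number of participants who worsened under each treatment. Label these results as unadjusted.
3. State that a non-significant difference on these components will not be reported as absence of psychiatric harm.

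This takes a few sentences and one small table from data already scheduled for collection, with no change to visits, treatment or stopping rules. The downside is about a 5% two-sided chance signal per component, half of it in the direction of harm. Across three components the chance of at least one signal in either direction is 1 − 0.95³ = 14% if they are independent. Labelling the results as unadjusted deals with this openly. No tolerability verdict should be hung on the upper confidence limit, because the plan sets no margin to judge it against.
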